13.5 Close-Out Visit (ISO 14155)

A close out visit will be conducted to ensure that the principal investigator's records are complete, all documents needed for the sponsor's files are retrieved, remaining clinical investigation materials are disposed of, previously identified issues have been resolved and all parties are notified. The visit will occur after the last subject's case report forms have been

May not be reproduced without written permission from PQ Bypass, Inc.
completed, study has been closed with reviewing IRB/IEC and all regulatory issues have been addressed.

13.6 Monitoring Reports (ISO 14155)

All monitoring activities shall be documented in a written report to the sponsor and shall include:

- a) the date, investigation site identification, name of the monitor and name of the principal investigator or other individuals contacted, and
- b) a summary of what the monitor reviewed and his/her observation(s) with regard to the completion of previous action items, significant findings, facts, deviations, conclusions, and recommended actions to be taken to secure compliance.

A copy of the monitoring report or a summary of key findings shall be shared with the principal investigator in writing.

14.0 STUDY ADMINISTRATION

PQ Bypass will make necessary efforts to ensure that this study is conducted in compliance with Good Clinical Practices (GCPs) and all applicable regulatory requirements.

14.1 Source Documentation

The Investigator must maintain detailed source documents on all trial subjects who are enrolled in the trial or who undergo screening. Source documents include subject medical records, hospital charts, clinic charts, Investigator's subject trial files, as well as the results of diagnostic tests (e.g., laboratory tests).

The following minimum information should be recorded in the subject's medical records:

- The date the subject entered the trial and the subject number
- The trial protocol number and the name of the Sponsor
- The date that informed consent was obtained
- Evidence that the subject meets trial eligibility requirements (e.g., medical history, trial procedures and/or evaluations)
- The dates of all trial related subject visits
- Evidence that required procedures and/or evaluations were completed
- Use of any concurrent medications
- Documentation of specific device used, if any
- Occurrence and status of any Adverse Events
- The date the subject exited the trial, and a notation as to whether the subject completed the trial or was discontinued, including the reason for discontinuation

14.2 Clinical Data Management

Software

This study will utilize electronic data capture (EDC), allowing the data to be entered directly into the computerized system by the clinical site personnel. The Medrio electronic data capture software will be used. This software was developed and validated by Medrio Incorporated. The specific study set up within the software will be the subject of user acceptance testing and is not released for use in the study until it has successfully passed this testing.

Security

Hosting is provided by Medrio Inc. and the data entered on the electronic case report forms (eCRFs) along with applicable metadata is transmitted using 128 bit SSL and 1024 bit RSA public keys. The server on which the data will be stored resides within a secure data center with security guards, electronic access controls and digital video monitoring as well as Cisco firewalls and advanced intrusion detection/prevention systems. Access to the study EDC system will be limited to authorized users with permission levels granted based on the user's role in the study. Each user is given a unique user ID and generate their own private

Query Management

Queries are generated and managed within the EDC system. Data checks, including those that detect missing or inconsistency entries, will be programmed into the system and will automatically be generated upon data entry. Manual queries may also be generated by the monitors, CRAs or data management personnel as necessary. Sites can respond to an automatic system generated query by making an update to the data and/or providing a textual response to the query. Query responses are reviewed and closed out by the monitor, CRA or data management personnel.

Database Closure and Export for Analysis

The primary clinical study report will be generated once all necessary patients have reached the primary efficacy follow up of 12 months. A database snapshot will be taken at this time for analysis. Data will be reviewed per the data snapshot checklist that will list the data cleaning activities required. All data is exported into SAS format for analysis by the study statistician and to be archived. Once all follow up has been completed and the database closure checklist completed, the EDC system study data and metadata will be exported and archived. All CRF data will be exported into SAS format for analysis and archive.

14.3 Criteria for Terminating Study

PQ Bypass reserves the right to terminate the study at any time, but intends only to exercise this right for valid scientific or administrative reasons related to protection of subjects. Investigators and associated EC and CA will be notified in writing in the event of termination.

Possible reasons for study termination include:

- The discovery of an unexpected, significant, or unacceptable risk to the subjects enrolled in the study
- A decision on the part of PQ Bypass to suspend or discontinue development of the device

14.3 Criteria for Suspending/Terminating a Study Center

PQ Bypass reserves the right to stop the screening of subjects at a study center at any time after the study initiation visit if no subjects have been enrolled or if the center has multiple or severe protocol violations without justification or fails to follow remedial actions.

Possible reasons for suspending/terminating a study center include, but are not limited to:

- Repeated failure to complete case report forms prior to scheduled monitoring visits
- Failure to obtain written Informed Consent
- Failure to report SAEs/UADEs to PQ Bypass within 24 hours of knowledge
- Loss of (or unaccounted for) investigational product inventory

14.4**Data Safety Monitoring Board (DSMB)**

A Data Safety Monitoring Board (DSMB) consisting of non Investigator experts, will review safety data from the study and establish stopping rules for early termination of the trial. The composition of the DSMB will include at least one statistician and at least two clinicians with expertise in the treatment interventional peripheral disease. Names of the actual members will not be announced. The frequency of the DSMB meetings will be determined in conjunction with the Sponsor. However, the DSMB may call a meeting at any time if there is reason to suspect safety is an issue.

The DSMB will make recommendations based upon the safety analysis of adverse events, protocol deviations, and device failures. The DSMB will function in accordance with SOPs and applicable regulatory guidelines.

The DSMB chairperson will notify PQ Bypass by confidential memo, of any safety or compliance issues. They will also provide confidential recommendations, when necessary, of study termination based upon the safety stopping rules determined at study onset, or because a clinically significant result was identified in safety analyses of the data. All DSMB reports will remain strictly confidential, but will be made available to regulatory authorities upon request.

15.0 PROTOCOL DEVIATIONS

A protocol deviation is defined as an event where the Investigator or site personnel did not conduct the study according to the protocol.

Investigators shall be required to obtain prior approval from PQ Bypass Clinical Director before knowingly deviating from the protocol, except where necessary to protect the life or physical well being of a subject in an emergency. Such approval shall be documented in writing and maintained in clinical study management and Investigator files. Prior approval is generally not expected in situations where unforeseen circumstances are beyond the Investigator's control, (e.g., subject was not available for scheduled follow up office visit, blood sample lost by laboratory, etc.); however, the event is still considered a deviation and will be reported via the appropriate CRF.

Deviations must be reported to PQ Bypass regardless of whether medically justifiable, pre approved by PQ Bypass or taken to protect the subject in an emergency. Subject specific deviations will be reported on the Protocol Deviation case report form. Non subject specific deviations, (e.g., unauthorized use of an investigational device outside the study, unauthorized use of an investigational device by a physician who has not signed an Investigator agreement or not been trained in the use of the device, etc.), will be reported to PQ Bypass. Investigators will also adhere to procedures for reporting study deviations to their EC and CA, where required, in accordance with their specific reporting policies and procedures.

Regulations require that Investigators maintain accurate, complete and current records, including documents showing the dates of and reasons for each deviation from the protocol.

16.0 REGULATORY CONSIDERATIONS**16.1 Maintaining Records**

The Sponsor will maintain copies of correspondence, data, shipment of devices, serious adverse device effects and other records related to the clinical trial.

16.2 Data Storage and Confidentiality

Study information will be kept in HIPAA compliant files or in secure databases with access protected by password. Neither subject names or other identifying information will be released from the site, nor will any identifying information be used in any published reports that are developed as a result of this study. De identified copies of relevant source documents for each study visit with privacy protected copies of electronic image files for X rays, DUS and CTA will be stored in secured files at PQ Bypass or at a validated data warehousing vendor.

16.3 Site Record Retention Policy

The Sponsor and clinical sites will maintain all records pertaining to this study for a period of seven years following the date on which the investigation is terminated or completed, or the date that the records are no longer required for purposes of supporting a regulatory submission. If the reviewing Ethics Committee or Competent Authority retention policy is longer than seven years, record retention will be mandated under those respective policies. Record retention dates will be provided to all concerned by the Sponsor.

16.4 Ethics Committee (EC) and Competent Authority (CA) Approval

The trial will only be started in a center after written approval of the protocol and Patient Informed Consent has been obtained from the appropriate Ethics Committee. Any amendment to the final protocol and informed consent should be submitted to the Ethics Committee.

Regulatory approvals must be obtained prior to enrolment of the first patient. The Sponsor will arrange EC and CA approvals for the study. The Sponsor or its designated CRO (HealthLink) will require a copy of any EC and CA correspondence, as well as the final approval letter from the EC and CA, where applicable.

No changes in the Clinical Investigation procedures will be effected without mutual agreement of the Principal Investigator and the Sponsor. The agreement of the changes must be documented by signing the corresponding Clinical Investigation Plan amendments.

All changes require notification to the EC/IRB and the CA (when appropriate), or approval where requested by local regulations. Substantial changes may require approval from the EC/IRB and the CA prior to implementation.

Substantial changes are changes which could:

- have an effect on the safety of the clinical investigation participants,

May not be reproduced without written permission from PQ Bypass, Inc.

- influence the interpretation of the documents on which the conduct of the clinical investigation is based, or
- influence the other requirements assessed by the ethics committee.

17.0 INVESTIGATOR RESPONSIBILITIES, RECORDS AND REPORTS**17.1 Investigator Responsibilities**

The Investigator is responsible for ensuring that this trial is conducted according to this protocol and that signed Informed Consent is obtained from each subject prior to his or her inclusion in this trial.

It is the Investigator's responsibility to ensure that all staff assisting with this trial have the appropriate qualifications and are fully instructed on the trial procedures and respect subject confidentiality, as specified in the Investigator Agreement with the Sponsor.

The Investigator is responsible for ensuring that the conduct of the trial conforms to the EC and CA requirements and provides all necessary communication with the EC and CA including, but not limited to, annual trial reports and required adverse event notifications.

17.2 Investigator Records**Case Report Forms**

The standardized Case Report Forms (CRFs) will be used to collect complete and accurate records of the clinical data from the trial according to the International Conference on Harmonization (ICH)/WHO Good Clinical Practice (GCP) standards. The Investigator is responsible for collecting and accurately recording the data generated for this trial.

Screening Log

Investigators will maintain a screening log that will record the date of informed consent, the date of screening, the enrollment status (enrolled/excluded) and the reason for exclusion for all screen failures.

17.3 Investigator Report

The final clinical report will be prepared and provided to each Principal Investigator for submission to their respective IEC after conclusion of the trial.

18.0**PUBLICATIONS**

The PQ Bypass publications policy for this Study is as follows. Following the earliest of a) publication of the multi center Study results, b) receipt of a notice from PQ Bypass stating that the multi center Study has been terminated or, c) twenty four (24) months after completion or termination of the Study at all Investigative sites, Investigators shall have the right to publish, in appropriate scientific journals or other professional publications, information and data collected or produced as a result of their participation in the Study, provided that drafts of the publications have been delivered to PQ Bypass for purposes of review and comment at least sixty (60) days prior to the first submission for publication or public release, to which Investigating Parties shall give due consideration. PQ Bypass shall return comments to the Investigator within forty five (45) days receipt of the draft. In addition, the Investigator shall delay any proposed publication/presentation in the event PQ Bypass so requests to enable PQ Bypass to secure patent or other proprietary protection. In all such publications, credit shall be given to PQ Bypass its sponsorship of the Study. Similarly, in publications by PQ Bypass regarding the Study, appropriate recognition will be given of the contribution made by the Institution and Principal Investigator, as applicable. PQ Bypass may use, refer to, and disseminate reprints of scientific, medical, and other published articles relating to the Study, including such reprints that disclose the name of Investigators and/or Institution.

19.0 DEFINITIONS

Acute Technical Success

See Technical Success

Adverse Device Effect

An adverse event related to the use of an investigational medical device. This definition includes adverse events resulting from insufficient or inadequate instructions for use, deployment, implantation, installation, or operation, or any malfunction of the investigational medical device. This definition also includes any event resulting from use error or from intentional misuse of the investigational medical device.

Adverse Event (AE)

Any untoward medical occurrence, unintended disease or injury, or untoward clinical signs (including abnormal laboratory findings) in subjects, users or other persons, whether or not related to the investigational medical device or index procedure. Adverse events are captured throughout the course of the study.

Allergic Reaction to contrast, polyester, nickel compound of the device and/or anesthesia

An overreaction of the body's immune system to a component of an investigational device (e.g., nitinol metal, polyester, plastics), contrast agents and/or anesthesia medication given to the subject for completion of a study related procedure (e.g., MSCT, angiogram, investigational device), which requires medical intervention to treat the allergic reaction.

Anesthesia Type

Type of anesthesia administered. Categorized as either general, local, or epidural/spinal.

Anticipated Adverse Device Effect (AADE)

An expected effect associated with endovascular treatment of the SFA and may occur during the procedure or during the course of the study. These anticipated effects have been previously identified in the risk analysis report.

Blood Loss

- **Blood loss \geq 1000 mL** – Defined as any blood loss \geq 1000 mL.
- **Estimated Procedural Blood Loss** - Defined as the total estimated blood loss (mL) during the index procedure. Includes blood loss resulting from adjunctive procedures performed during the index procedure.

Contrast Volume

Total volume of contrast (mL) administered during the index procedure. Includes contrast administered for adjunctive procedures performed during the index procedure.

Death

Death is divided into two categories and will be reported anytime in a subject's study participation.

- **Device or procedure related death** - Death related to the Study Device or to any procedure (index or subsequent) intended to treat the target vessel.

- **Non-device or procedure related death** – Death NOT related to any procedure (index or subsequent) intended to treat the target vessel or death not related to the Study Device.

Device Deficiency

Inadequacy of the Study Device with respect to its identity, quality, durability, reliability, safety or performance. Device deficiencies include malfunctions, use errors, and inadequate labeling.

Device Time

Number of minutes from initial Study Device insertion to final Study Device removal. It does not include time needed to perform adjunctive procedures.

Explant

Removal of the Study Device implant for any reason.

Estimated Procedural Blood Loss

See Blood Loss

Fluoroscopy Time

Total fluoroscopy time (minutes) used during the index procedure and includes time utilized for adjunctive procedures performed during the index procedure.

Intensive Care Unit Time

See post procedure ICU time

Life Expectancy > 1 Year

The duration of time the test subject is expected to survive post procedure. Subjects must not have a concurrent medical condition that would cause expected survival to be less than one year.

Longer-Term Technical Success (1-year)

See Technical Success

Major Adverse Event (MAE)

Composite endpoint of the following: defined as all death, TLR or any amputation of the index limb to 30 days (± 7 days). See individual events for detailed definitions.

Myocardial Infarction (MI)¹⁰

Typical chest pain and either a Q wave or non Q wave MI as described below.

- **Q-Wave Myocardial Infarction** – Development of new, pathological Q waves in two or more contiguous leads V1 V3 or Q Wave ≥ 3 ms in width in leads I, II, aVL, AVF, V4, V5 or V6 and ≥ 1 mm in depth on at least two serial ECGs.
- **Non-Q-Wave Myocardial Infarction** – (1) Non procedural (pre procedural or > 30 days post index procedure, endovascular or surgical intervention) – CK MB elevation ≥ 2 times the

¹⁰ Myocardial infarction redefined--a consensus document of The Joint European Society of Cardiology/American College of Cardiology Committee for the redefinition of myocardial infarction. Eur Heart J. 2000 Sep;21(18):1502-13. Review.

May not be reproduced without written permission from PQ Bypass, Inc.

upper limit of normal in the absence of new pathological Q waves, (2) post index procedure or endovascular re intervention (≤ 30 days) – CK MB elevation ≥ 3 times the upper limit of normal in the absence of new pathological Q waves, or (3) post Surgical intervention (< 30 days) – CK MB elevation ≥ 5 times the upper limit of normal in the absence of new pathological Q waves.

Post-Procedure ICU Time

Number of hours a patient is in an intensive care unit prior to discharge or moving to a step down or standard care unit.

Primary Assisted Patency

Patency following endovascular re intervention at the target vessel site in case of symptomatic restenosis.

Primary Patency

No significant reduction of flow detectable by Duplex ultrasound (DUS) through the index lesion. Significant reduction of flow was determined as binary restenosis, defined as a peak systolic velocity ratio (PSVR) ≥ 2.5 as measured by DUS.

Post-Procedure Length of Hospital Stay

Number of days from the end of the procedure until the patient is discharged from the hospital. This does not include time spent in a skilled care facility.

Procedure Time

Number of minutes needed to perform the index procedure from time of initial vessel cut down time to time of final guidewire removal. Also referred to as skin to skin time.

Renal Failure

Need for dialysis or a laboratory finding of serum creatinine > 3.5 mg/dL.

Respiratory Failure

The need for mechanical ventilation beyond the first 24 hours post index procedure (and/or re intervention) or the need for re intubation or ventilator support after the first 24 hours (unless the subject was ventilator dependent pre procedure).

Secondary intervention

Any visit to the operating room or catheterization laboratory subsequent to the PQ Bypass Stent Graft implant procedure to treat an adverse event related to the disease, the index procedure or the study device.

Secondary Patency

Patency of the target lesion after treatment of a (re)occlusion of the index lesion.

Serious Adverse Event (SAE)

Any undesirable event occurring which led, could have led or might lead either directly or indirectly to the death or serious deterioration in the health of a subject, user or another person, regardless of whether the event was caused by the medical device.

Stroke or Transient Ischemic Attack (TIA)

- **Stroke** - A new neurological deficit lasting more than 24 hours, or lasting 24 hours or less with a brain imaging study showing infarction.
- **TIA** - A neurological deficit lasting less than 24 hours and, if an imaging study is performed, shows no evidence of infarction. These events may occur anytime throughout a subject's study participation and may or may not require intervention.

Stent Graft Occlusion

Complete blockage of blood flow through the Stent Graft as determined by traditional imaging (e.g. DUS, CTA, MRA or Angiography).

Stent Graft Placement Accuracy

Estimated distance (mm) from the operator's intended target as compared to the actual position placed as assessed via angiography during the index procedure.

Target Lesion Revascularization (TLR)

A re intervention of the index lesion site.

Target Vessel Revascularization (TVR)

Treatment of another lesion at the target vessel site but no the index lesion itself.

Technical Success, Acute

Successful delivery of PQ Bypass Stent Graft System to the identified area and successful removal of delivery system.

Unanticipated Adverse Device Effect (UADE)

An adverse device effect which by its nature, incidence, severity or outcome has not been identified in the risk analysis report.

Vascular Access Type

Method of entry into the vascular system. Categorized as either surgical cut down or percutaneous.

20.0

REFERENCES

- ¹ American Heart Association. What is PAD? Available at: http://www.heart.org/pr nt_presenter.jhtm ? dent f er=3020249. Accessed June 3, 2013.
- ² National Institutes of Health. National Heart, Lung, and Blood Institute. Diseases and Conditions Index. What is Atherosclerosis? Available at: <http://www.ncbi.nlm.nih.gov/health/conditions/atherosclerosis/WhatIs.htm>. Accessed June 3, 2013.
- ³ Chi Y and Jaff M. Optimal risk factor modification and medical management of the patient with peripheral arterial disease. *Catheterization and Cardiovascular Interventions*. 2008;71(4):475-89.
- ⁴ Bashir R and Cooper C. Evaluation and medical treatment of peripheral arterial disease. *Current opinion in cardiology*. 2003;18(6):436-43.
- ⁵ Gornik H and Beckman J. Peripheral Arterial Disease. *Circulation*. 2005;111:e169-e172.
- ⁶ Alber M, Romiti M, Brochado-Neto FC, et al. Meta-analysis of alternate autologous veins bypass grafts to infrapopliteal arteries. *J Vasc Surg*. 2005;42:449-55.
- ⁷ TASC Classification Consensus Document on PAD – 2000.

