May not be reproduced without written permission from PQ Bypass, Inc.

- ¹ Use of retrospective assessments, prior to signing of informed consent, were used if they were performed as routine standard of care
- ² Brief physical examination at baseline was targeted to assess limb schema and concurrent medical conditions to assess subjects' eligibility for study participation. Health status assessments were performed at discharge and subsequent clinical visits to assess for limb schema and other changes in medical conditions that are reportable as adverse events
- ³ CK at discharge time point was obtained only if subject shows signs or symptoms of cardiac schema. CK MB levels required for CK to be elevated ($\geq 2X$ the laboratory upper limit of normal) if CK and CK MB were elevated, and acute myocardial infarction was diagnosed, the subject will be treated according to hospital procedures
- ⁴ 30 day ECGs performed if subject experiences any schema symptoms since discharge
- ⁵ Angiography performed both pre procedure and post procedure to record data needed for percent diameter stenosis and other measures. Additional angiography may be performed at investigator discretion or to assess events
- ⁶ Duplex ultrasound to be completed at each visit
- ⁷ At baseline Category Scale, during follow-up, both Clinical Category and Clinical Improvement Rutherford Becker Scores
- ⁸ Perform Toe Brachal Index (TBI) only if unable to reliable assess ABI reading. Tests are performed in resting state. Post procedure follow-up assessments depend on which test was performed pre procedure
- ⁹ Pavulox recommended for one year post procedure; ASA is recommended for all subjects indefinitely

Patient Screening, Enrollment and Follow-Up

¹ If procedure rescheduled, final eligibility (e.g., labs, imaging) will need to be reconfirmed.

Change History

Revision Letter	Change Description
A	Initial Release
A1	Amendments per Austrian EC requests
B	
 • Lesion length adjustment • Clinical outcome data update • Device description update • Statistical Plan update from 30 to 60 evaluable patients • Risk benefit update • Addition of x-ray at 12 month follow-up • Minor editorial updates
B1	Added "Section 18 PUBLICATIONS" as requested by Latvian Authorities
B2	Updated statistical plan rationale per Italian EC request using superiority hypothesis instead of a non-inferiority

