5.2 Study Endpoints

Primary Safety Endpoint:

The primary safety endpoint for this study is freedom from a major adverse event (MAE) at 30 days post procedure. An MAE is defined as TLR, amputation of the treated limb, or death.

Primary Effectiveness Endpoint:

The primary effectiveness endpoint is defined as stent patency as evidenced by a peak systolic velocity ratio (PSVR) < 2.5 from DUS obtained within the 12 month visit window with no clinically driven re intervention within the stented segment.

Secondary Safety Endpoints:

Secondary safety endpoints will be evaluated and include:

1. The combined rate of death at 30 (± 7) days, target lesion revascularization (TLR), index limb amputation, and an increase in Rutherford Becker Classification by 2 classes (comparing pre to post procedural assessments) at 12 months.
2. Major adverse vascular event (MAVE) at 30 days, 6 months (180 ± 14 days) and 12 months (360 ± 30 days) defined as stent thrombosis, target limb amputation, clinically apparent distal embolization, defined as causing end organ damage (e.g. lower extremity ulceration, tissue necrosis, or gangrene), procedure related arterial rupture, acute limb ischemia, or bleeding event requiring transfusion.
3. The combined rate of serious procedural adverse events, including death, myocardial infarction, index limb amputation, and access site and treatment site complications requiring surgery, blood transfusion (>2 units of PRBC), or prolonged hospital stay within 30 days of the index procedure.

Secondary Effectiveness Endpoints:

1. Acute technical (lesion) success, procedural success and device success.
2. Ankle Brachial Index (ABI) and Toe Brachial Index (TBI) at 1, 6 and 12 months.
3. Target vessel revascularization (TVR) at 6 and 12 months.
4. Limb ischemia by Rutherford Becker Classification at Baseline, 1, 6, and 12 months.
5. Number of any type of index limb amputations at 6 and 12 months.
6. Absolute Claudication Distance as measured by the Exercise Tolerance Test (TASCI) assessed in 100 subjects at baseline, 1, 6, and 12 months.
7. Target lesion revascularization (TLR) at 1, 6 and 12 months.

8. The rate of primary assisted patency through follow up defined as: revascularization of non occlusive (<99%) stenosis within the stent graft or immediately above or below the treated arterial segment with less than 50% residual stenosis.

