9.4 Discharge Evaluation

The discharge evaluation is described in the schedule of events table. CK at discharge is to be obtained only if subject shows signs or symptoms of cardiac ischemia. CK MB is required if CK is elevated ($\geq 2X$ the laboratory upper limit of normal).

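### Section 19 requires typical chest pain for every MI, which is narrower than the trial's own ischemia work-up, and its printed Q-wave width of 3 ms excludes almost nothing

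*Combined protocol and SAP*

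**What the plan says.** Section 5.2, secondary safety endpoint 3, is "The combined rate of serious procedural adverse events, including death, myocardial infarction, index limb amputation" and certain access-site and treatment-site complications, within 30 days of the index procedure. The primary MAE composite and MAVE do not include MI, so this is the only endpoint that counts it. Section 11.1 summarizes the other secondary endpoints with point estimates and 95% score bounds. The Protocol Summary gives adjudication of secondary safety endpoints to an independent committee or medical reviewer.

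Section 19 defines MI as follows:

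- Entry condition for every MI: "Typical chest pain and either a Q wave or non Q wave MI as described below".
- Q-wave MI, first lead group (V1 to V3): "Development of new, pathological Q waves in two or more contiguous leads".
- Q-wave MI, second lead group: "Q Wave ≥ 3 ms in width in leads I, II, aVL, AVF, V4, V5 or V6 and ≥ 1 mm in depth", followed by "on at least two serial ECGs". No enzyme rise is required.
- Non-Q-wave MI within 30 days of the index procedure: "CK MB elevation ≥ 3 times the upper limit of normal in the absence of new pathological Q waves".

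The work-up is set elsewhere. Section 9.4 says "CK at discharge is to be obtained only if subject shows signs or symptoms of cardiac ischemia", and CK-MB follows if CK is at least 2 times the upper limit of normal. Footnote 3 to the Schedule of Assessments repeats this and foresees an acute MI diagnosed when both enzymes are raised; it does not mention chest pain. The schedule marks an ECG at baseline, discharge and 30 days. Footnote 4 puts a condition on the last of these only: "30 day ECGs performed if subject experiences any schema symptoms since discharge" (the garbled word is evidently ischemia).

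**The concern.** The definition and the work-up use different clinical conditions. The work-up looks for ischemia however it presents; the definition then accepts only ischemia that presents as typical chest pain. The trial can therefore hold enzyme or ECG evidence of an MI that its own rule will not count. The population makes this foreseeable: Section 2.1 says that patients with PAD may have asymptomatic as well as symptomatic coronary disease, and puts their risk of heart attack or stroke at three to six times that of patients without PAD.

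The Q-wave limb raises a separate doubt. A width threshold should separate pathological Q waves from trivial ones, and 3 ms hardly does so. The requirement that the Q wave be new is written in front of the first lead group and may or may not carry over to the second. Old Q waves can be present at entry, because Section 5.6 does not exclude prior MI and inclusion criterion 13 in Section 5.5 allows an earlier coronary intervention.

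At stake is the reported 30-day rate of serious procedural events, in a study small enough for a single event to show.

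**Working it through.** The plan states no figure on this point, so there is none to reproduce. The check has three parts.

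**1. Definition against work-up.** Four cases, read literally:

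| Case (within 30 days of index procedure) | Evidence collected? | MI under Section 19? |
|---|---|---|
| A. Signs or symptoms of ischemia, no typical pain, CK-MB at least 3 times the upper limit | Yes, through Section 9.4 | No: entry condition fails |
| B. No typical pain, new Q waves on the discharge ECG | Yes, discharge ECG is scheduled without a condition | No: entry condition fails |
| C. Typical pain, old Q wave at least 1 mm deep in the second lead group on the baseline and discharge ECGs, no enzyme rise | Yes | Yes, if the newness requirement does not reach the second group |
| D. Typical pain, CK-MB at least 3 times the upper limit | Yes | Yes either way; the Q-wave limb changes only the MI type |

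A and B are possible under-counts and follow directly from the text. C is a possible over-count and depends on how an ambiguous sentence is read.

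**2. The width.** Input: 3 ms (Section 19). The documents give neither paper speed nor sampling rate, so both are assumed.

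- Width on paper = time × speed. At 25 mm/s: 0.003 × 25 = 0.075 mm. At 50 mm/s: 0.003 × 50 = 0.15 mm. The depth criterion beside it is 1 mm. One millimeter across the paper is 40 ms at 25 mm/s and 20 ms at 50 mm/s.
- Digital samples = time × rate. At 250, 500 and 1000 Hz: 0.75, 1.5 and 3 samples.

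So 3 ms cannot be read on paper at these speeds and is marginal digitally. As a criterion it excludes almost no Q wave.

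**3. Size.** Input: 60 evaluable subjects (Section 5.4). One subject moves the composite by 1/60 = 1.67 points if that subject has no other component event, and by nothing otherwise.

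The Wilson (score) limits for x composite events in n = 60, with p = x/n, are

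[p + z²/(2n) ± z√(p(1−p)/n + z²/(4n²))] / (1 + z²/n).

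For x = 1 and z = 1.96, the upper limit is (0.01667 + 0.03201 + 1.96 × 0.02324) / 1.06403 = 8.86%.

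| Composite events in 60 | Rate | Two-sided 95% interval | One-sided 95% upper bound |
|---|---|---|---|
| 0 | 0.0% | 0.0 to 6.0% | 4.3% |
| 1 | 1.7% | 0.3 to 8.9% | 7.1% |
| 2 | 3.3% | 0.9 to 11.4% | 9.6% |
| 3 | 5.0% | 1.7 to 13.7% | 11.9% |

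Both versions are shown because Section 11.1 does not say whether the bounds for these endpoints are one-sided or two-sided. Over this range one event gained or lost moves the upper limit by about 2.3 to 2.8 points. The counts are for the whole composite, and MI is only one of its components.

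**The case against.** The strongest reply is that this is a wording mismatch and a possible misprint in a descriptive secondary composite. Much of that stands.

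- **The printed width may not be the plan's.** The text was extracted with many lost characters, and a missing digit cannot be excluded. A reader might infer a factor-of-ten slip, but no value other than 3 ms is in the documents, so none can be asserted.
- **A reader might infer that MIs are miscounted in both directions.** That is not shown. An over-count still needs typical chest pain, 1 mm depth, two serial ECGs and independent adjudication. The opening words of the Q-wave limb can also be read to govern both lead groups, and the non-Q-wave limbs turn on the absence of new pathological Q waves, which favors that reading.
- **A reader might infer that any sign or symptom starts the cardiac work-up.** It does not. CK needs signs or symptoms of cardiac ischemia, CK-MB needs a raised CK, and the 30-day ECG needs ischemic symptoms.
- **A reader might infer that an ECG cannot resolve 3 ms.** That holds for reading paper at the assumed speeds, not for every digital recording.
- **The events do not disappear.** MI is a listed potential adverse event in Section 12.0, SAEs go to the sponsor within 24 hours whatever their cause (Sections 12.2 and 12.6), and the DSMB reviews safety data. What is lost is the MI label in the one endpoint that uses it.

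None of this removes the conflict between the chest-pain condition and the work-up trigger, or makes a 3 ms width useful as a criterion.

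**Conclusion.** The point holds in limited form. The under-count follows from the text: an enzyme-positive MI without typical pain is one that the protocol sets out to detect and Section 19 then cannot count. The over-count is only a literal possibility, resting on the non-discriminating width and on the unclear reach of the newness requirement.

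The size is up to 1.7 points per misclassified subject in 60, provided that the subject has no other component event. The documents do not say how often MI occurs without typical pain, so no expected number of misclassified events can be given. No hypothesis test or success criterion depends on the endpoint. The statement about the width assumes paper speeds of 25 to 50 mm/s and assumes that 3 ms is what the source document prints.

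**What to change.** In Section 19, and in the adjudication form to match:

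1. Check the Q-wave width against the consensus document cited in the definition, and correct it if it is misprinted. No value is proposed here.
2. State that the Q wave must be new against the baseline ECG in both lead groups.
3. Reconcile the chest-pain condition with the trial's own trigger in Section 9.4 and footnote 3 to the Schedule of Assessments. The reconciled wording should go no further than that trigger. If a new ECG change alone were accepted as a qualifying sign, a new Q wave would satisfy both the clinical and the ECG condition, and Q-wave MI would have no clinical condition left.

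The cost is a few wording changes, with no new test or visit. The downside is that the reported MI rate may be slightly higher.
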